NCT Number: NCT02739412

Official Title: Efficacy of Low Dose, SubQ Interleukin-2 (IL-2) to Expand Endogenous Regulatory T-Cells in Liver Transplant Recipients

Document Type: Protocol with Statistical Analysis Plan

Document Date: 09/07/2017

PART B STUDY DESCRIPTION

TITLE OF PROTOCOL	Efficacy of Low Dose, Subcutaneous Interleukin-2 (IL-2) to Expand Endogenous Regulatory T-Cells in Liver Transplant Recipients
Principal Investigator	[name]

B1. PURPOSE OF PROTOCOL

The primary objectives of this pilot study are:

1. To assess the efficacy of very low dose subcutaneous interleukin-2 (IL-2) to promote regulatory T cell (Treg) expansion in a cohort of liver transplant recipients with stable graft function, no active or history of auto-immune diseases, no evidence of allograft rejection, no current evidence of viral hepatitis, and no advanced liver graft fibrosis.
2. To assess the safety and tolerability of very low dose IL-2 in a liver transplant recipient cohort.

Secondary objectives:

1. To investigate the percent change of peripheral blood Treg cells and change in phenotype and function of Treg cells in response to very low dose IL-2 in a liver transplant recipient cohort.
2. To identify patients who are IL-2 responsive and thereby potential candidates for withdrawal of immunosuppression. This pilot study will not involve withdrawal of immunosuppression (IS), however if it is determined that low dose IL-2 is safe, well tolerated, and results in significant expansion of Treg cells, then subsequently a follow-up study of IL-2 expansion of Treg cells followed by IS withdrawal will be proposed.
3. Assess short term impact of study treatment on subject's DSA status, i.e. change in DSA titers or development of de novo DSA.

Exploratory Objective:

1. Establish baseline phenotypic values for T cell exhaustion in the trial cohort.
2. Determine if IL-2 treatment results in development of IL-2 antibodies in the study population

B2. SIGNIFICANCE AND BACKGROUND FOR THE STUDY

Transplantation remains the most successful treatment for end-stage liver disease (ESLD), but the need to administer life-long immunosuppression (IS) to prevent rejection limits patient and graft survival. Systemic immunosuppression is associated with the development of significant morbidity from complicating side effects of hypertension, hyperglycemia and hyperlipidemia contributing to the metabolic syndrome and cardiovascular disease, cerebrovascular disease and renal failure. Additionally, long-term use of immunosuppression is associated with a remarkably increased risk of skin and other malignancies. Long-term survival following liver transplantation is still suboptimal, and liver recipients exhibit higher morbidity and mortality than the general population. This is mainly due to comorbidities arising in large measure from chronic IS treatment.

Liver transplantation is the only organ transplant setting in which a sizeable proportion of patients spontaneously develop "operational tolerance", a phenomenon defined by the maintenance of stable graft function in the absence of destructive immune responses without the need of IS. Withdrawal of IS is feasible in selected patients who develop spontaneous operational tolerance, and may overcome the problems of exposure to long term IS. Unfortunately, this phenomenon only occurs many years after transplantation (i.e. 79% of adult patients >11 years post-transplant, but in 0% of adult patients <50 years old and <6 years post-transplant), when irreversible IS-related toxicity has

often already occurred. Therefore, there is an urgent need to develop strategies to intentionally induce tolerance in young liver recipients who have been transplanted for a short period of time.

Immunological tolerance is regarded as an active regulatory process whose outcome depends on the balance between cytopathic lymphocytes and graft-protecting, regulatory T cells (Tregs). In animal models of transplantation, liver allografts are spontaneously tolerated through regimens that are dependent on CD4+CD25+Foxp3+ T cells (Tregs). In human liver recipients undergoing IS withdrawal years after transplantation, transient intra-hepatic lymphocyte infiltration with preferential accumulation of Tregs is also observed. This suggests that a shift in the balance between regulatory and effector T cells is critical to achieve tolerance, and that IS withdrawal provides a window of opportunity to do so.

IL-2 is essential for the survival and function of Tregs. In animals, inefficient IL-2 signalling results in Treg deficiency and autoimmunity, whereas administration of IL-2 in vivo induces Treg expansion and immunoregulation. Deficient IL-2 signaling is a hallmark of human autoimmune diseases such as type-1 diabetes. Calcineurin inhibitors (CNI), which constitute the mainstay IS in liver transplantation, reduce the overall availability of IL-2. Studies have determined that in liver recipients on CNI, Tregs are reduced in number as a consequence of increased apoptosis. Low-dose IL2 reverses this phenotype by upregulating the anti-apoptotic BCL-2 gene selectively in Tregs thereby promoting Treg expansion. Tregs, cells that bear high affinity IL-2 receptors, require IL-2 to expand and maintain their immunosuppressive phenotype. Tregs not only expand in blood, but also in peripheral tissues, with the largest increase being observed in the liver.

Recent clinical studies using low dose IL-2 in patients with drug resistant GVHD and certain forms of autoimmunity demonstrated that low doses IL-2 (1 million units/m²) is safe and efficacious with a 50% response rate in GVHD. Clinical studies performed to date show that even very low doses of IL-2, i.e., 0.3 million units/m², expands Tregs whereas doses of 1million units/m² also expanded the number of pro-inflammatory innate immune cells bearing intermediate affinity IL-2Rs. Expansion of pro-inflammatory cells could counteract, to some degree, the immunoregulatory effects of IL-2 driven expansion of Tregs. Therefore, this lower dose (0.3 million IU/m²) would potentially limit this unwanted consequence and boost both efficacy and safety. The affinity of Tregs for IL-2 is much higher than innate immune cells except for a tiny, desirable population of highly IL-2 responsive immunoregulatory NK cells. Additionally, in recent studies of cynomolgus monkey renal transplant recipients, with durable drug free graft survival, rejection was incited by daily treatment with 1 million IU/ m². IL-2 induced an unwanted expansion of memory T cells. Taken together, the results in clinical and monkey studies indicate that in treatment with 1 milion IU/ m² IL-2, levels of IL-2 hover in a range where Tregs expand, but this is accompanied by unwanted activation of innate immune cells and/or T-memory, such that the stimulatory effect on Tregs is offset, sometimes moderately, sometimes markedly, by activation and expansion of inflammatory innate and memory T cells.

In consideration of these most recent findings, we amend the protocol (version date 9.7.2017), to reduce the dose of IL-2 (from 1.0 million to 0.3 million units/m²) to expand Tregs, at a dose that does not expand pro-inflammatory immune cells to further improve the safety profile while still promoting tolerance.

This provides additional rationale for administering a very low-dose IL-2 to liver transplant recipients to expand the pool of endogenous Tregs and shift the balance between effector and regulatory lymphocytes at the time IS drugs are discontinued.

To maximize the benefit derived from IS withdrawal, there is a need to find strategies to intentionally induce tolerance in young recipients in whom accumulated IS toxicity has not yet occurred. Tregs can suppress cytopathic immune responses and inhibit transplant rejection. In contrast to innate immune cells and effector T cells, resting Tregs constitutively express the high affinity IL-2 receptor, making Tregs exquisitely sensitive to very low-doses of IL-2. This protocol proposes to employ low-dose IL-2 to promote the selective expansion of endogenous Tregs and shift the balance between effector T cells and Tregs. Studies have revealed that successful IS discontinuation is associated with a

transient intra-graft immune regulatory response with preferential accumulation of Treg cells. This suggests that short-term enhancement of Treg numbers and/or function at the time of IS withdrawal may facilitate the acquisition of tolerance in patients who are not predisposed to spontaneously develop it. IL-2 is a cytokine that is essential for the optimal development, survival and function of Tregs. Several clinical studies have shown that low-dose IL-2 preferentially expands Tregs and is safe and efficacious in patients with autoimmunity or graft versus host disease (GVHD). In these studies, Treg frequency increased up to 2 to 8-fold without significant changes in the number of effector T cells. Our objective is to investigate if administration of a short-course of low-dose IL-2 to liver transplant recipients facilitates an increase in peripheral blood Treg cells. We propose to conduct this pilot study to assess safety and efficacy of IL-2 in expanding peripheral blood Treg cells and assess the effect of IL-2 on T effector cells and cell of the innate immune response in these transplant recipients.

The primary objectives of this pilot study are:

1. To assess the efficacy of very low dose subcutaneous interleukin-2 (IL-2) to promote regulatory T cell (Treg) expansion in a cohort of liver transplant recipients unlikely to be safely withdrawn from IS in the absence of other treatment with stable graft function, no active or history of auto-immune diseases, no evidence of allograft rejection, no current evidence of viral hepatitis, and no advanced liver graft fibrosis.
2. To assess the safety and tolerability of very low dose IL-2 in a liver transplant recipient cohort;
3. Assess short term impact of study treatment on subject's DSA status, i.e. change in DSA titers or development of de novo DSA.

Secondary objectives:

1. To investigate the percent change of peripheral blood Treg cells and change in phenotype and function of Treg cells in response to very low dose IL-2 in a liver transplant recipient cohort;
2. To identify patients who are IL-2 responsive and thereby potential candidates for withdrawal of immunosuppression. This pilot study will not involve withdrawal of immunosuppression (IS), however if it is determined that very low dose IL-2 is safe, well tolerated, and results in significant expansion of Treg cells, then subsequently a follow-up study of IL-2 expansion of Treg cells followed by IS withdrawal will be proposed.

Exploratory objective:

1. Establish baseline phenotypic values for T cell exhaustion in the study cohort.
2. Determine if IL-2 treatment results in development of IL-2 antibodies in the study population

References:

Benítez C. Multicenter clinical trial of immunosuppression withdrawal in liver transplantation. *Hepatology* 2013;58(5):1824-35

Bohne F. Intra-graft gene expression predicts the development of tolerance in liver transplantation. *J Clin Invest* 2012;122(1):368-82

Hartemann A. Low-dose interleukin-2 in patients with type-1 diabetes. *Lancet Diabetes Endocrinol* 2013 Dec;1(4):295-305.

Koreth J. Interleukin-2 and Regulatory T Cells in GVHD. *N Engl J Med*. 2011;365(22):2055-66

Matsuoka K. Interleukin-2 restores regulatory T cell homeostasis in chronic GVHD. *Sci Transl Med* 2013;5(179):179ra43

B3. DESCRIPTION OF RESEARCH PROTOCOL

[figure not shown]
A. Study Design – Overview, Methods, Procedures

The study is a single arm, prospective, open label efficacy trial of a 4 week course of low dose subcutaneous IL-2 (1MIU/mL/m²/day) to expand peripheral blood regulatory T cells (Tregs) in a liver transplant population..

This pilot trial will treat up to 10 liver transplant recipients who are ≤65 years of age, a minimum of 2 years but no more than 4 years post primary liver transplantation for non-autoimmune conditions, have had no evidence of transplant rejection, and have no current evidence of liver allograft dysfunction or viral hepatitis.

Study objectives include (1) determine the efficacy of the administration of low dose IL-2 to promote Treg cell expansion; (2) assess the safety and efficacy of low dose IL-2 in a liver transplant recipient cohort; (3) investigate the percent change of peripheral blood Treg cells and change in phenotype and function of Treg cells in response to low dose IL-2 in a liver transplant recipient cohort.

Study Scheme:

Study Procedure:

Screening (S0):

After obtaining informed consent the following screening procedures will be completed:

- Full history and medical record review
- Physical examination including height and weight
- Vital signs (blood pressure, heart rate and temperature)
- Blood (approximately 20 milliliters) will be drawn for
 - ✓ liver function panels (AST, ALT, ALP, Bilirubin, Albumin) and kidney function panels (Na, K, Cl, CO₂, Creatinine, Glucose, Ca) if not previously obtained within 1 month of screening
 - ✓ viral hepatitis and autoimmune panels (HBV sAg, HCV Ab, ANA, ASMA IgG) if not previously obtained within 6 months of screening
 - ✓ serum pregnancy test for women of child bearing potential (WOCBP)
- Fibroscan if liver biopsy/fibroscan results not obtained within 1 year of screening
- ECG if not obtained within 3 months of screening

Subjects with liver panel results <2xULN, serum creatinine <1.5 ULN; no evidence of viral hepatitis or

autoimmunity, no evidence of pregnancy, absence of advanced liver fibrosis, no history of seizure disorder and no evidence of cardiac disease will proceed with the study (see Inclusion/Exclusion criteria in section below).

Baseline/Treatment Visit Day 1 (W0):

Subjects will return to clinic to complete baseline measures and begin study treatment:

- Review of any new health problems, current medication and vital sign measures;
- Blood draw (approximately 35 milliliters) for
 - ✓ CBC with differential,
 - ✓ liver and kidney function panels,
 - ✓ immune cell counts ,
 - ✓ T cell exhaustion phenotyping,
 - ✓ serum IL-2 levels,
 - ✓ CNI trough levels,
 - ✓ presence of donor specific antibodies (DSAs)
 - ✓ presence of anti-IL-2 antibodies

Treatment: Subjects will start very low dose **IL-2 subcutaneous injections at a once per day dose of 0.3 million IU/mL per square meter body surface area (BSA) for 4 weeks.** Study staff will instruct subjects and/or identified care providers (e.g. friend or spouse) on subcutaneous injection technique.

The first study dose will be administered in the BIDMC Harvard-Thorndike Clinical Research Center. Subjects will remain in house for 2 hours of observation to monitor drug tolerability and adverse events.

Subjects will be given a paper calendar to record their self-administration of the study drug. Subjects will record the time of injections each day and bring the study calendar and all unused drug to all study visits. (see Calendar attached)

Treatment (D3):

Subjects will return to clinic on Day 3 for evaluation of adherence to treatment and staff observation of proper injection technique (for Dose 3) and the following measures will be obtained:

- Review of any new health problems, current medications
- Vital signs
- Blood draw (approximately 10 milliliters) for liver and kidney function panels

Treatment (W1, W2, W3, W4)

Subjects will return to clinic weekly until Day 28 (Week 4). Subjects will receive a refill of IL-2 (not at Week 4 visit) and the following measures will be obtained:

- Review of any new health problems, current medications, vital signs and weight,
- ECG,
- Blood draw (approximately 35 milliliters) will be drawn for
 - ✓ CBC with differential,
 - ✓ liver and kidney function panels,

- ✓ serum IL-2 levels,
- ✓ immune cell counts (Weeks 2 and 4)
- ✓ Week 4 only: CNI trough levels and serum pregnancy test (WOCBP)
- ✓ DSAs (Week 4)
- ✓ anti-IL-2 antibodies (Week 4)

Subjects will discontinue IL-2 treatment after Day 28 (Week 4).

Subjects will have blood drawn for standard of care labs at Week 4, i.e. CBC, liver and kidney panels, and CNI trough levels. We will obtain standard of care results from subjects' medical records and draw extra blood (approximately 25 ml) for research testing for DSA and anti-IL-2 antibodies (week 4), serum IL-2 levels and PBMCs flow cytometry and a serum pregnancy will be conducted for WOCBP.

Follow-up (W8, W12, W36)

Subjects will return to clinic for post-treatment follow-up at Weeks 8, 12 and 36. The following measures will be obtained:

- Review of any new health problems, current medications, vital signs and weight,
- Full physical examination will be completed at end of study (Week 36);
- Review standard of care lab results for
 - ✓ CBC with differential,
 - ✓ liver and kidney function panels,
 - ✓ CNI trough levels,
- Blood draw (approximately 20 milliliters) for study labs
 - ✓ Immune cell counts (Weeks 8 and 12)
 - ✓ serum IL-2 levels (Weeks 8 and 12)
 - ✓ serum pregnancy test for WOCBP (Weeks 8 and 12).
 - ✓ anti-IL-2 antibodies (Week 36)

Dosage Reduction and Treatment Withdrawal

The dose of IL-2 may be reduced by half to 0.15 million IU /m² daily if a subject experiences untoward side effects. If symptoms improve, the dose may be re-escalated to target. If symptoms persist, the dose frequency may be reduced to every other day administration or the Investigator may discontinue study treatment.

Study treatment will be discontinued in the presence of any of the following circumstances:

- ✓ Subject withdraws consent
- ✓ Life threatening anaphylactic reaction to IL-2
- ✓ Life threatening infection on IL-2
- ✓ The Investigator may discontinued study treatment in the presence of other clinically significant findings including abnormal ECG, blood panel results >2x ULN and/or other signs of significant toxicities.

Subjects who are withdrawn from treatment will complete remaining study visits and continue to receive follow-up care from his/her BIDMC transplant Hepatologist.

Standard of Care Maintenance Immunosuppression: Eligible patients must be receiving stable dosing of immunosuppressant therapy for a minimum of 1 month prior to study enrollment. Maintenance immunosuppression is customize to the patient but typically, stable liver transplant patients at 2-4 year post transplant who are otherwise eligible to enroll into this trial would be taking tacrolimus (target 12 hour trough goal of 4-6ng/mL) with or without mycophenolic acid (as mycophenolate mofetil or mycophenolate sodium) at a dose between 500-1000mg twice a day.

Safety Monitoring

The PI is ultimately responsible for protecting the rights, safety and welfare of subjects enrolled into the trial. Study visits will be conducted weekly during the treatment phase of the trial; post treatment follow-up visits will be conducted at week 8 and 12. The PI will review all safety parameters including clinical safety laboratory assessments within 48 hours of completion of the measure. Clinical laboratory values that fall outside of the pre-specified safety ranges will be brought to the PIs attention the day the reports are final to assess clinical significance.

Patients of the Transplant Institute have direct access to Transplant Nurse Coordinator consultation 24/7/365. Transplant Coordinators will alert the PI or designee for any study subject who calls with questions or concerns.

Patients will be given a Study Information card and instructed to present it to any health care provider they see during the time that are participating in the trial. The Study ID card will include a brief description of the trial, name of the study drug, and PI contact information. See safety card attached.

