The drug manufacturer Novartis has conducted 7 Phase I/II clinical trials in 235 patients with a variety of doses and schedules using subcutaneous IL-2. Dosages have ranged from 2 million IU per day to 9 million IU per day. The study populations included metastatic renal cell carcinoma, advanced malignancy, and chronic lymphocytic lymphoma. In these trials, the following adverse events were recorded:

- Pyrexia (fever) – 77%
- Rigors (shivering) – 68%
- Asthenia (tiredness) – 49%
- Anorexia (loss of appetite) – 54%
- Nausea – 50%
- Vomiting – 49%
- Diarrhea – 40%
- Headache – 35%
- Dry skin – 25%
- Rash – 24%
- Injection site inflammation – 24%
- Dyspnea (shortness of breath) – 24%
- Injection site reaction – 24%
- Cough – 23%
- Myalgia (muscle pain) – 23%
- Insomnia – 21%
- Hypokinesia (muscle rigidity) – 20 %
- Dizziness – 18%
- Abdominal pain – 16%
- Injection site pain – 14%

- Depression – 11%
- Pruritus (itchiness) – 10%
- Oliguria (decrease in urine production) – 9%
- Confusion – 8%
- Hypotension (low blood pressure) – 7%
- Anxiety – 6%
- Increased serum creatinine – 4%
- Tachycardia (increased heart rate) – 3%
- Gastrointestinal bleeding – 2%
- Arrhythmia (unusual heart beat) – 1%
- Myocardial infarction (heart attack) – <1%
- Kidney failure – <1%

The most common serious adverse event associated with **high dosage, IV administered IL-2** is capillary leak syndrome where capillary permeability increases and serum proteins and fluids move to the extravascular space. In subcutaneous administration of IL-2, capillary leak syndrome is much less frequent and less severe. In the Novartis clinical trials of **subcutaneous IL-2**, no cases of pulmonary edema were recorded. Peripheral edema occurred in 14% of patients and unspecified edema occurred in 11% of patients.

IL-2 has not been approved for use for the indication being tested in this study. In this study we will test the efficacy and safety of low dose IL-2, i.e., 0.3 million IU per square meter body surface area (BSA) given once a day in subcutaneous injections, to liver transplant patients over a 4 week period of time to measure the effect on the number of peripheral Treg cells.

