HIPAA standards. Access to clinical medical records used for the trial is strictly limited in accordance with hospital policies. Data abstracted from medical records will be managed in compliance with GCP clinical research best practices; both hard copy and electronic data collected for the investigation will be stored in restricted access files in the TI Clinical Research Offices and in electronic files and folders behind hospital firewalls. Data included in analytic files will be de-identified and the key linking data to patient identity will be maintained by the investigators in a separated restricted access location.

B9 Multi-Site Studies

Is the BIDMC the coordinating site? Yes No

Is the BIDMC PI the lead investigator of the multi-site study? Yes No

B10 Dissemination of Research Results

The study investigators will inform participants directly of the results of their individual treatment response (responder or non-responder) to IL-2.

Study ID Card

PATIENT SAFETY CARD – PLEASE KEEP IN YOUR WALLET

I am participant in a clinical research study. Study treatment is 4 weeks daily low dose subcutaneous Proleukin® (recombinant IL-2), manufactured by Prometheus Laboratories.

Name: _____ DOB: _____

Address: _____ Phone: _____

Emergency Contact (1): _____ Phone: _____

Emergency Contact (2): _____ Phone: _____

Liver Transplant Patient – Beth Israel Deaconess Medical Center (BIDMC)

PATIENT SAFETY CARD – PLEASE KEEP IN YOUR WALLET

Study Treatment and Investigator Contact

Proleukin® Dose: 0.3×10^6 units/m² SC daily (duration 4 weeks)

Physician Principal Investigator: [name], BIDMC
Transplant Institute.

You can contact him or an on call Transplant Nurse Coordinator 24/7

[contact].

Study IRB Reference #: 2016P-000086

Clinicaltrials.gov NCT# NCT 02739412

Calendar for Medication Recording

April 2016 (United States)

S	M	T	W	T	F	S
1	2	3	4	5	6	7
8	9	10	11	12	13	14
15	16	17	18	19	20	21
22	23	24	25	26	27	28
29	30	31				

Sun	Mon	Tue	Wed	Thu	Fri	Sat
27 <small>Easter Sunday</small>	28	29	30	31 <small>● 3rd Quarter</small>	1	2
3	4	5	6	7 <small>● New Moon</small>	8	9
10	11	12	13 <small>Thomas Jefferson's Birthday</small>	14 <small>○ 1st Quarter</small>	15	16
17	18	19	20	21	22 <small>○ Full Moon</small>	23
24	25	26	27	28	29 <small>● 3rd Quarter</small>	30

Click on Sign to add text and place
signatures on a PDF file.

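### The Day 1 treatment instruction and the design overview state the IL-2 dose in IU/mL per m², which defines no amount of drug, while the other dose statements give an amount per m²

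*Combined protocol and SAP*

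**What the plan says.** The daily dose of IL-2 is stated in six places in the combined protocol and SAP.

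- **B2, amendment rationale:** the amendment is made "to reduce the dose of IL-2 (from 1.0 million to 0.3 million units/m²".
- **B3.A, Study Design overview:** the course is "low dose subcutaneous IL-2 (1MIU/mL/m²/day".
- **B3.A, Baseline/Treatment Visit Day 1, Treatment:** subjects start on a "once per day dose of 0.3 million IU/mL per square meter body surface area (BSA", continued for four weeks.
- **B3.A, Dosage Reduction and Treatment Withdrawal:** "The dose of IL-2 may be reduced by half to 0.15 million IU /m² daily" if side effects occur.
- **B5, risks of IL-2:** the study tests "0.3 million IU per square meter body surface area (BSA) given once a day in subcutaneous injections".
- **Study ID Card:** 0.3 × 10⁶ "units/m² SC daily (duration 4 weeks".

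The supplied text gives no injection volume, vial strength, dilution or preparation step.

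**The concern.** Two of the six statements carry a per-millilitre term and four do not. One of the two is the Day 1 paragraph, the only place in the visit-by-visit procedures that tells the reader what daily dose to start. Read literally, it gives a concentration scaled by body surface area, and such a quantity cannot be administered until a volume is attached.

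This matters because subjects or a care provider give most of the injections themselves. Of the 28 daily doses, only the first (given in the research centre) and the third (technique observed in clinic) are stated to be given or watched by staff. The trial's conclusions about Treg expansion and tolerability attach to a named dose, so that dose should be expressed as an amount, in the same way wherever it appears.

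The overview adds a conflict of number to the conflict of unit. The two are separate: changing the overview's number would leave its unit wrong, and the Day 1 paragraph has the unit problem although its number agrees with B2, B5 and the card.

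**Working it through.** No sample-size or power formula applies. The check is of units, then of numbers.

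**Step 1. Set the statements side by side.**

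| Place | Number | Unit | Defines an amount once BSA is known? |
|---|---|---|---|
| B2, amendment rationale | 0.3 million (from 1.0) | units/m² | Yes |
| B3.A, overview | 1 million | IU/mL/m²/day | No |
| B3.A, Day 1 treatment | 0.3 million | IU/mL per m², once per day | No |
| B3.A, dose reduction | 0.15 million (half) | IU/m² daily | Yes |
| B5, risks | 0.3 million | IU per m², once a day | Yes |
| Study ID Card | 0.3 million | units/m² daily | Yes |

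**Step 2. Carry the units through.** Let S be body surface area in m² and V the injected volume in mL.

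- Amount per m²: 0.3 million IU/m² × S m² = 0.3S million IU. This is a dose.
- Day 1 wording: 0.3 million IU/mL/m² × S m² = 0.3S million IU/mL. This is a concentration. The dose is 0.3S × V million IU, and V is not stated.

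The Day 1 wording gives the same dose as the per-m² wording if V = 1 mL of a solution whose strength is scaled to S. It also does so if the solution is 0.3 million IU/mL and the volume is 1 mL per m², because then V = S and the dose is again 0.3S. So there are natural readings with no discrepancy in dose, but each supplies a volume that the text does not give.

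**Step 3. Check the dose-reduction rule.** It calls 0.15 million IU/m² half of the dose, so the full dose it assumes is 2 × 0.15 = 0.30 million IU/m². That matches B2, B5 and the card in number and unit. It matches the Day 1 paragraph in number only, and the overview in neither.

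**Step 4. Check the numbers.** The overview's 1 million against 0.3 million elsewhere is a ratio of 1/0.3 = 3.3.

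**Step 5. Check the worked example in B5.** For an 82 kg person the high-dose comparison reproduces: 0.6 × 82 = 49.2 million IU, and 49.2 × 3 = 147.6 million IU per day. The protocol dose for the same person is given as 1.95 million IU per day.

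- At 1.0 million IU/m²: 1.95/1.0 = 1.95 m², plausible at 82 kg. The Mosteller formula gives 1.91 to 2.05 m² for assumed heights of 160 to 185 cm.
- At 0.3 million IU/m²: 1.95/0.3 = 6.5 m², which is not possible.

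The example therefore follows the overview's number, not the 0.3 million figure. It is expressed as a total in IU, with no per-millilitre term. It states no body surface area.

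**The case against.** The strongest reply is that the intended unit is clear. Four of the six statements use an amount per m², and so does the B5 account of the earlier dose-escalation trial. The dose-reduction rule sits in the same section as the Day 1 paragraph and implies a full dose per m². The patient-held card, which states the dose, uses an amount per m². On this view the per-millilitre term is a stray. Much of this stands: a careful reader would probably arrive at an amount per m². It does not make the Day 1 paragraph coherent, and the same term in the overview means that it is not confined to one sentence.

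Safeguards are also relevant. Staff instruct subjects in injection technique, visits are weekly during treatment, and unused drug and the dosing calendar come back at each visit. These are opportunities to notice a wrong volume and they lower the risk. A check of returned drug, however, needs an expected volume to compare against.

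Third, a volume may be stated elsewhere. Figures are missing from the supplied text and no pharmacy document is included. That stands, so the finding cannot be that dispensing instructions do not exist. The unit conflict is on the page either way.

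Finally, nothing says that the pharmacy or the subjects work from the Day 1 paragraph. That is correct, and the point does not depend on it. Nor does the dose-reduction rule contradict itself: it gives an amount per m², and whether volume or strength is halved is a preparation detail.

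**Conclusion.** The protocol expresses its study dose in two incompatible kinds of unit. The Day 1 treatment paragraph and the design overview use a concentration per body surface area with no volume. B2, the dose-reduction rule, B5 and the card use an amount per m². The overview also carries a number 3.3 times that in B2, the Day 1 paragraph, B5 and the card. This conclusion rests only on the wording and on the absence of a volume from the supplied text.

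A reader might infer that the Day 1 wording would deliver about half the dose. The documents do not support that. The figure requires everyone to receive a flat 1 mL of a 0.3 million IU/mL solution, which assumes a volume and ignores the per-square-metre term in the sentence itself. At 1.95 m² it compares 0.30 with 0.3 × 1.95 = 0.585 million IU, or 51%, but the readings in Step 2 that keep the surface-area term also give 0.585. The 1.95 m² is itself back-calculated from the B5 example at 1.0 million IU/m², the level that the amendment rationale says is being replaced; at 0.3 million the example gives 6.5 m². For the same reason, the closeness of the half-dose figure to the 0.15 million reduced level is no evidence of a hazard: it only reflects division by a surface area near 2.

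The point is therefore an internal inconsistency in the dose unit of a largely self-injected drug. It should be corrected, but no size of misdosing can be attached to it and none is shown to have occurred.

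**What to change.** Reconcile the unit in the B3.A overview and the Day 1 treatment paragraph with B2, the dose-reduction rule, B5 and the Study ID Card, and state the dose in a single amount unit throughout. If the per-millilitre term was meant to describe a prepared concentration, state that concentration separately from the dose. Reconcile the overview's number with the other statements in the same revision, and check the B5 worked example alongside it. Which dose is right is for the sponsor to settle.

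The unit correction is a wording change in two places. It adds no visits, subjects or analyses.
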